8.3 Sample Size Justification

The number of subjects for each treatment	t (ZuraPre	p™	1		,	Chlo	oraPrep®
and ZuraPrep™	Vehicle)	is	based	off	of	the	following
assumptions: the primary efficacy paramete	ers are as	def	ined abo	ove;	the	powe	er is 80%;
and the ATEs (as approximated by mear	n reduction	ns	from ba	aseli	ne)	and	standard
deviations of the ATEs are equivalent to	the results	S					

Page 31 of 53 Zurex Pharma, Inc. Project: ZX-ZP-0092 Microbac Protocol: 865.1.03.25.18

Microbac Project: 865-107

all other components/ingredients remain consistent . Using the standard normal approximation, this requires 65 subjects per treatment. The number 108 was used to make randomization blocking easier and to be conservative. See Appendix 14.12 for the full Estimation of Sample Size report.

8.4 Subject Discontinuation Criteria

A summary and/or listing of reasons for discontinuation will be provided.

8.5 Procedures for Accounting for Missing Data and Protocol Deviations

Missing data will be reported as missing. No imputation will be performed. Calculations that use missing data points will still be performed if the calculation is still logically possible.

Other irregularities or deviations which could affect the results will be handled on a case-by-case basis. Handling will be documented in the statistical report.

8.6 Deviations to Statistical Plan

Any deviation(s) from the original statistical analysis plan will be described and justified in the final report.

9. Monitoring

Zurex Pharma, Inc., as sponsor of this study along with the Investigator, is responsible for ensuring the proper conduct of the study with regard to protocol adherence and validity of the data recorded on the source documents and eCRFs. Zurex Pharma, Inc. has, therefore, assigned a study monitor to this study. The progress of the study will be monitored by:

- Periodic on-site review
- Telephone communications and e-mail
- Review of eCRFs and source documents

The Investigator will give the Zurex Pharma, Inc. study monitor direct access to source documents that support data on the eCRFs and make available such records to authorized Zurex Pharma, Inc., quality assurance, IRB, and regulatory personnel for inspection and/or copying.

Note: The Federal Privacy rule (HIPAA) specifically permits the use and disclosure of protected health information "to a person subject to the jurisdiction of the Food and Drug Administration (FDA) [e.g., study sponsor] with respect to an FDA-related product or activity for which that person has responsibility, for the purpose of activities related to the quality, safety, or effectiveness of such FDA-regulated product or activity" [45 CFR 164.512(b)(1)(iii)].

Page 32 of 53 Zurex Pharma, Inc. Project: ZX-ZP-0092 Microbac Protocol: 865.1.03.25.18

Microbac Project: 865-107

10. Quality Control and Quality Assurance

Zurex Pharma, Inc. and the Investigator are responsible for implementing and maintaining quality assurance and quality control systems through written standard operating procedures (SOPs) to ensure that this study is conducted and data are generated, documented and reported in compliance with the protocol, GCP and regulations cited in Section 1.4 of this protocol. Study monitoring may be carried out to accomplish this.

11. Ethics

This study will be conducted in accordance with the principles that have their origin in the Declaration of Helsinki, 21 CFR 50 (Informed Consent) and 56 (IRBs). Laboratory operations will be conducted in accordance with 21 CFR 58 (Good Laboratory Practice for Nonclinical Laboratory Studies).

The study will start only after approval of the protocol and consent form by the IRB. The approval letter or notice must contain the IRB name and identification number, meeting date, and sufficient information to identify the protocol and informed consent by name and number that were reviewed. Zurex Pharma, Inc., prior to study initiation, must receive a copy of the IRB approval letter.

12. Data Handling and Record Keeping

12.1 Study Personnel

Prior to study initiation, the Investigator must provide Zurex Pharma, Inc. with a signed Investigator agreement as documentation of the Investigator's commitment to conduct the study according to the protocol and all applicable state and federal regulations.

12.2 Pre-Study Documentation Requirements

Prior to study initiation, the Investigator must provide Zurex Pharma, Inc. with the following documents:

- Signed protocol including any amendments in place prior to study initiation
- Curriculum vitae for the Investigator and any co-Investigators
- IRB-approved informed consent form containing subject authorization for use and disclosure of Protected Health Information statement.
- IRB study approval letter (including approval of the protocol, consent form, Investigator and study facility)
- IRB name, location and board membership listing
- Signed Investigator agreement
- Signed Study Agreement and Confidentiality agreement

Page 33 of 53 Zurex Pharma, Inc. Project: ZX-ZP-0092 Microbac Protocol: 865.1.03.25.18

Microbac Project: 865-107

12.3 Completion of Electronic Case Report Forms

The primary source document for this study will be the subject's data capture form. The source documents will be retained at the site.

For this study, an electronic data management system (EDMS) will be used for the collection of the study data in an electronic format. The EDMS will be designed based on the protocol requirements, the approved eCRF layouts and specifications, and in accordance with 21 CFR Part 11. The eCRF layouts and specifications define and identify the applicable source data that will be collected and captured into the EDMS. The applicable source data will be electronically transcribed by the site designee onto the eCRF (data entry screens) in the EDMS. The investigator is ultimately responsible for the accuracy of the data entered into eCRFs. Data monitoring and management will be performed in the EDMS by the study clinical monitor.

12.4 Final Report

The Investigator will prepare a final study report. The final report will be a record of the total study conduct and will be subject to review by Zurex Pharma, Inc. The final report will assess and summarize all data collected and include: test material identification, type of assay, randomization schedule, dates of study initiation and completion, and data demonstrating neutralization effectiveness. A review of the final report by Quality Assurance, including compliance statements will also be included with the final report. A copy of the final report will be sent to the study sponsor.

14.2 Study Summary

[figure not shown]
Pre-Study	Screening Phase		Treatment Phase			
Preparation	14 Day Washout Period	Screening Day	Abdominal Region	dominal Region Groin Region		
Staff reviews study protocol	Initiation of consenting process	Complete Screening Inclusion/ Exclusion Criteria form	Complete Treatment Inclusion/ Exclusion C	criteria form		
Prepare consent form	Review study Consent Form and Inclusion/ Exclusion Criteria	Visual skin assessment	Visual skin assessme	kin assessment		
Obtain IRB approval	Review subject instructions	Collect screening baseline samples from abdominal and groin regions	Mark test areas, Collect baseline samp	oles		
Recruit volunteers for screening phase (14 day washout / screening day)	Subject signs consent form	Count screening plates, determine which volunteers qualify for study	Apply test articles			
Prepare subject kits	Visual skin assessment (abdominal and groin regions) Dispense subject kits	Contact and enroll eligible subjects, schedule Treatment Day Schedule for clipping, if needed, 48 hrs. prior to Treatment Day	Visual skin assessment, 30 seconds (± 5 sec.) and 6 hours (± 30 min.) post-prep sample	Visual skin assessment, 30 seconds (± 5 sec.) and 6 hours (± 30 min.) post-prep sample		
	Schedule for clipping, if needed, 48 hrs. prior to screening visit	visit No bathing / showering 72 hrs. prior to Treatment Day visit	Count Treatment Day Baseline plates, determine qualification and enroll additional subjects as required	Count Treatment Day Baseline plates, determine qualification and enroll additional subjects as required		
	No bathing / showering 72 hrs. prior to screening visit			,		

Page 37 of 53 Zurex Pharma, Inc. Project: ZX-ZP-0092

Microbac Protocol: 865.1.03.25.18 Microbac Project: 865-107

14.3 Abdomen and Groin Diagram

Follow the randomization scheme for each subject for the exact placement of study materials.

Page 38 of 53 Zurex Pharma, Inc. Project: ZX-ZP-0092 Microbac Protocol: 865.1.03.25.18

Microbac Project: 865-107

14.4 Randomization Scheme Example

Abdo	minal and Gro	in Sites Bilate	eral Samplir	ng Procedure	Configuration	ons	
		G	ROUP 1				
Key: A =	ZuraPrep™						
-			/ti	t 1\			
	ChloraPrep®			control)			
C =	ZuraPrep™	Vehi	cle (negative	control)			
Subject	Left Treatment	Right Treatment	Site 1	Site 2	Site 3	Site 4	
1001				l			
1002							
1003							
1004							
1005							
1006							
1007							
1008							
1009			Subjects w	vill be numbered	l seguentially f	rom 1001 to	
1010	Treatment		the numl	ber of subjects	treated during	the study.	
1011	block 1		Randomiz	zation will be pe		oup issued	
1012				prior to stud	dy initiation.	1.	
1013							
1014							
1015							
1016				0			
1017				Sample or	der group 1		
1018	Treatment						
1019	block 2						
1020							
1021							
1022							
1023							
1024							
		1					

Page 39 of 53 Zurex Pharma, Inc. Project: ZX-ZP-0092 Microbac Protocol: 865.1.03.25.18

Microbac Project: 865-107

14.6 Subject Instructions – Washout, Screening Visit, Treatment Visit

Page 42 of 53
Zurex Pharma, Inc. Project: ZX-ZP-0092
Microbac Protocol: 865.1.03.25.18

Microbac Project: 865-107

14.7 Treatment Application Instructions

Treatment Site Application Instructions

Abdominal Test Site

- 1. Using repeated back-and-forth strokes of the sponge for thirty (30) seconds, completely wet the treatment area with test material.
- 2. Allow the area to air-dry for three (3) minutes. Do not blot or wipe away.

Inguinal Test Site

- 1. Using repeated back-and-forth strokes of the sponge for two (2) minutes, completely wet the treatment area with test material.
- 2. Allow the area to air-dry for three (3) minutes. Do not blot or wipe away.

Page 43 of 53 Zurex Pharma, Inc. Project: ZX-ZP-0092 Microbac Protocol: 865.1.03.25.18

Microbac Project: 865-107

[figure not shown]
Treatment Site Application Instructions

Abdominal Test Site

- 1. Using repeated back-and-forth strokes of the sponge for thirty (30) seconds, completely wet the treatment area with test material.
- 2. Allow the area to air-dry for three (3) minutes. Do not blot or wipe away.

Inguinal Test Site

- 1. Using repeated back-and-forth strokes of the sponge for two (2) minutes, completely wet the treatment area with test material.
- 2. Allow the area to air-dry for three (3) minutes. Do not blot or wipe away.

Treatment Site Application Instructions

Abdominal Test Site

- 1. Using repeated back-and-forth strokes of the sponge for thirty (30) seconds, completely wet the treatment area with test material.
- 2. Allow the area to air-dry for three (3) minutes. Do not blot or wipe away.

Inguinal Test Site

- 1. Using repeated back-and-forth strokes of the sponge for two (2) minutes. Completely wet the treatment area with test material.
- 2. Allow the area to air-dry for three (3) minutes. Do not blot or wipe away.

Page 44 of 53 Zurex Pharma, Inc. Project: ZX-ZP-0092 Microbac Protocol: 865.1.03.25.18

Microbac Project: 865-107

14.8 Confirmation of Release and Receipt of Study Materials

Test Site: Microbac Lal	5-107 poratories, Inc., [name],	, [name]	
Quantity (Units)	Description	ID/Lot Number	Exp
(OIIIIS)	·	Number	 
Supplies Released to Site			
	Sponsor Signature		
Supplies Sent to Site (Dat	e):		
`	,		_
Supplies Checked and Ve			
	Signature		1

Page 45 of 53 Zurex Pharma, Inc. Project: ZX-ZP-0092 Microbac Protocol: 865.1.03.25.18 Microbac Project: 865-107

14.10 Procedure for Neutralization Validation

1. Background

The density of normal human skin flora generally ranges from 10² to 10⁵ CFU/cm² depending on the body site. However, since significant neutralizer or toxic effects are more easily detected at a lower cell density, the efficacy and toxicity of this neutralizer system will be assessed against a lower bacterial concentration.

This is a test where the study materials are applied to the abdomen and the treated areas will be sampled. After sampling, a selected representative of normal skin flora will be added into a portion of each sample. Each sample will then be processed using procedures in accordance with ASTM E1054-08 (2013).

2. Objective

This control assay will determine the ability of the SS to completely neutralize the active ingredients in the test treatments when applied to the abdomen by recovering and quantifying microorganism populations on agar media and is appropriate for antimicrobial agents that can be chemically inactivated or diluted to sub-inhibitory levels.

Neutralization validation will be conducted prior to the conduct of efficacy testing.

3. Subject Entry Criteria

subjects will be used for the neutralization validation required for this study. Each subject must meet the inclusion and exclusion criteria described in Sections 4.1 and 4.2 except for the baseline bacterial count, the 72-hour exclusion from showering/bathing and the length of the washout period. No minimum bacterial count is required and the washout period is only necessary for 7 days (not 14 days). The subjects will be asked to provide information on demographics and inclusion/exclusion criteria and sign the Consent and Authorization Forms before beginning the 7-day washout period. When the subjects return to begin their participation in the study they will again be asked to provide information relative to inclusion/exclusion criteria. If they meet all inclusion/exclusion criteria, they may be enrolled. The subjects will be identified by the letter "N" for neutralization and a subject number of

The test, vehicle and reference control articles will be applied to the abdomen regions using bilateral applications so that applications are performed for each treatment using bilateral

Page 47 of 53 Zurex Pharma, Inc. Project: ZX-ZP-0092 Microbac Protocol: 865.1.03.25.18

Microbac Project: 865-107

application One area will be located on one side of the body and the remaining area on the other side.

The treatments per subject will be randomized. The randomization scheme will be generated before the test.

4. Test Organisms

The test organisms for this study are:

- a.
- 5. Treatment Materials
 - a. ZuraPrep™ (containing 70% v/v Isopropyl Alcohol)
 - b. ChloraPrep® (reference control article containing 2% chlorhexidine gluconate)
 - c. ZuraPrep™ Vehicle (negative control article)
- 6. Materials, Supplies and Equipment

See section 3.4.3 of the Microbac 865-107 Protocol. In addition, 70% v/v isopropyl alcohol swabs.

7. In-vivo Test Procedures (collection of samples)

Preparation of Test Area and Post-Prep Sampling: Neutralization samples will be taken from the abdomen. The subject number, location of the prep application, location of the sites sampled within the prep area, and the time of sample collection will be documented on the appropriate data capture form. The subject will be treated with the study materials based on the following.

- For each side of the body, mark the abdominal test areas using a sterile 1.5" x
 5" template. The 1.5" x 5" areas will be delineated with each containing two 1" x 1" sampling site.
- After the test areas are marked, each area will be processed using three 70% isopropyl alcohol swabs for a total of one minute to prepare the site; the areas will be allowed to dry. This step is to prepare the skin for the neutralization test.
- Prep the test areas with the appropriate treatment according to the instructions provided in Appendix 14.7, Microbac 865-107 Protocol for groin.
- Using the scrub cup technique at approximately 30 seconds post-prep, begin collecting samples from each of two sampling sites within each test area using

Page 48 of 53 Zurex Pharma, Inc. Project: ZX-ZP-0092 Microbac Protocol: 865.1.03.25.18

Microbac Project: 865-107

SS by two technicians simultaneously. This technique is described in Section 5.2.1 of the Microbac 865-107 Protocol.

8.		ro Test Procedures (performed using the collected samples in accordance with ASTM 4-08 (2013))			
	8.1	Inoculur	m Preparation:		
		culture approxir such tha	th test organism, the organism will be prepared from and overnight broth $(24 \pm 4 \text{ hours})$ grown in TSB at $35 \pm 2\text{C}$ to yield a concentration of mately will be culture will be diluted using PBW in a manner will be delivered into the neutralizer tube (a aliquot bllected SS sample will be used).		
	8.2	Test:			
		•	the reference to test article applies to test article, the vehicle and the ce control article; all procedures outlined, where applicable will employ all)		
		8.2.1	Neutralizer effectiveness (Test 1):		
		а	Out of the aliquot of sampling solution taken from the volunteer, will be transferred to a new sterile tube and inoculated with the challenge microorganism so that the final concentration will equal colony-forming units (CFU) / mL of the challenge microorganism (the prepared inoculum will be diluted using PBW to achieve the desired concentration, aliquot from the dilution will be used).		
		b	Within one min after the addition of the challenge microorganism, the microorganisms will be enumerated by standard microbiological methods extant in the laboratory.		
		С	Triplicate aliquots will be removed and plated using TSA+N pour plates.		
		d	After 30 minutes, the microorganisms will be enumerated a second time using the same procedures.		
		е	Triplicate aliquots will be removed and plated using TSA+N pour plates.		
		8.2.2	Neutralizer toxicity (Test 2):		
		а	A aliquot of sampling solution will be inoculated with the challenge microorganism so that the final concentration will equal colony-		

manner as Test 1.

forming units (CFU) / mL of the challenge microorganism in the same

Page 49 of 53 Zurex Pharma, Inc. Project: ZX-ZP-0092 Microbac Protocol: 865.1.03.25.18 Microbac Project: 865-107

- b Within one min after the addition of the challenge microorganism, the microorganisms will be enumerated by standard microbiological methods extant in the laboratory.
- c Triplicate aliquots will be removed and plated using TSA+N pour plates.
- d After 30 minutes, the microorganisms will be enumerated a second time using the same procedures.
- e Triplicate aliquots will be removed and plated using TSA+N pour plates.
- f This procedure will be repeated two times for a total of three replicates.

8.2.3 Test microorganism viability control (Test 3):

- a A aliquot of PBW will be inoculated with a volume of the challenge microorganism so that the resulting suspension contains CFU/mL in the same manner as Test 1.
- b Within one min the microorganisms will be enumerated (in triplicate) by standard microbiological methods extant in the laboratory.
- c Triplicate mL aliquots will be removed and plated using TSA pour plates.
- d After 30 minutes, the microorganisms will be enumerated a second time using the same procedures.
- e Triplicate aliquots will be removed and plated using TSA pour plates.
- This procedure will be repeated two times for a total of three replicates.

8.2.4 Test article control (Test 4):

- a A aliquot of the test or control article will be inoculated with a volume of the challenge microorganism so that the resulting suspension contains CFU/mL in the same manner as Test 1.
- b Within one min the microorganisms will be enumerated (in triplicate) by standard microbiological methods extant in the laboratory.
- c Triplicate mL aliquots will be removed and plated using TSA pour plates.
- d After 30 minutes, the microorganisms will be enumerated a second time using the same procedures.

Page 50 of 53 Zurex Pharma, Inc. Project: ZX-ZP-0092 Microbac Protocol: 865.1.03.25.18

Microbac Project: 865-107

е	Triplicate	mL aliquots	will be	removed	and	plated	using	TSA	pou
	plates.								

f This procedure will be repeated two times for a total of three replicates.

8.3 Incubation:

All plates for Tests 1, 2, 3 and 4 will be incubated for 72±4 hours at 30°±2°C.

8.4 Interpretation of data:

- a. The number of surviving challenge microorganisms for each replicate from each test will be average count of the three plates.
- b. The number of survivor values will be transformed to log₁₀.
- c. The number of survivors (log₁₀) from each test (1, 2, and 4) will be compared to the test microorganism viability population (test 3).
- d. Neutralization aspects of the sampling solution will be considered adequate if the mean log₁₀ CFU/mL of Test 1 is not more than 0.20 log₁₀ less than the mean log₁₀ CFU/mL of Test 3 (Mean log₁₀ CFU/mL from Test 3 Mean log₁₀ CFU/mL from Test 1 using corresponding time points).
- e. The sampling solution will be considered non-toxic if the mean \log_{10} CFU/mL of Test 2 is not more than 0.20 \log_{10} less than the mean \log_{10} CFU/mL of Test 3 (Mean \log_{10} CFU/mL from Test 3 Mean \log_{10} CFU/mL from Test 2 using corresponding time points).
- f. The mean log₁₀ CFU/mL from Test 4 must be at least 0.20 log₁₀ less than the mean log₁₀ CFU/mL of Test 3.
- g. The amount of CFU added for each aspect must be confirmed to yield a final suspension containing CFU/mL (validated in test 3).
- h. The sterility controls must be negative for growth.

8.5 Controls:

8.5.1 Sterility control:

Triplicate plates of TSA and TSA+N used will be incubated with the test. In addition, triplicate aliquots of sampling solution and PBW will be plated using TSA pour plates used for a particular test date. All plates will be incubated with the test.

Page 51 of 53 Zurex Pharma, Inc. Project: ZX-ZP-0092 Microbac Protocol: 865.1.03.25.18

Microbac Project: 865-107

8.5.2 Challenge microorganism confirmation:

In order to confirm growth consistent with the challenge microorganism, Gram stains will be performed from a representative colony from a test plate. The colony morphology will be noted as well.

Page 52 of 53 Zurex Pharma, Inc. Project: ZX-ZP-0092 Microbac Protocol: 865.1.03.25.18

Microbac Project: 865-107

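### Neutralizer validation (Appendix 14.10): native skin bacteria in the treated-skin washings count as surviving challenge organisms, and their removal is never verified, so any residue biases Test 1 towards a pass

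*Combined protocol and SAP*

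**What the plan says.** All references are to Appendix 14.10 unless stated.

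- **Sample.** Test 1 (8.2.1) uses sampling solution collected from a volunteer's treated abdomen. Section 1 states: "After sampling, a selected representative of normal skin flora will be added into a portion of each sample". Triplicate aliquots are plated on TSA+N within one minute and again after 30 minutes.
- **Comparator.** Test 3 (8.2.3) puts the same challenge into buffered water (PBW), so it contains no skin bacteria.
- **Count.** Item 8.4(a) treats the average of the three plates as the number of surviving challenge organisms. No subtraction or exclusion of colonies is described.
- **Criterion.** Item 8.4(d) begins "Neutralization aspects of the sampling solution will be considered adequate if the mean" and then requires Test 1 to be no more than 0.20 log10 below Test 3 at the matching time. There is no upper limit on Test 1.
- **Steps that lower native flora.** Section 7 says "each area will be processed using three 70% isopropyl alcohol swabs for a total of one minute to prepare the site". It continues: "Prep the test areas with the appropriate treatment according to the instructions provided in Appendix 14.7, Microbac 865-107 Protocol for groin". In Appendix 14.7 those instructions are two minutes of application and three minutes of drying.
- **Checks.** The sterility control (8.5.1) covers the agars, sampling solution and PBW. The identity check (8.5.2) is: "Gram stains will be performed from a representative colony from a test plate", with colony morphology also noted.
- **Validation subjects.** Section 3 waives the 72-hour bathing restriction and says "No minimum bacterial count is required". It sets no maximum either.

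**The concern.** Test 1 colonies are challenge survivors plus any native bacteria that outlast the alcohol swab and the treatment. Test 3 colonies are challenge only. With a one-sided limit, native colonies can only help Test 1 pass.

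The identity check looks at one colony, and the challenge is itself a skin-flora organism. Whatever that stain shows, it does not change the count that enters 8.4(d).

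This is the plan's only stated verification that the antimicrobials stop acting once the sample is collected. Section 5.2.5 requires it before the study starts, and Sections 3.2.2 and 6.1.2 say there are no study validity criteria. If an inadequate neutralizer passed, residual active could go on killing in the tube or on the plate, and the 30-second counts for ZuraPrep or ChloraPrep would be too low. The vehicle comparison (margin 1.2) would be flattered. Unequal carry-over between the two actives would shift the non-inferiority comparison (margin 0.5).

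**Working it through.** **The limit as a recovery.** The 0.20 log10 limit is a chosen criterion, so there is no derivation to reproduce. It converts to 10^-0.20 = 0.631. Test 1 must reach 63.1% of Test 3, and a true loss of up to 36.9% is accepted.

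**Inputs.** C is the challenge concentration. It is redacted, so 30, 50 and 100 CFU/mL are assumed. r is true recovery of the challenge, and b is native CFU/mL in the washing.

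**Break-even b for a pass.**

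1. Native cells unaffected by the residue: rC + b ≥ 0.631C, so b = (0.631 − r)C.
2. Native cells killed in the same proportion: r(C + b) ≥ 0.631C, so b = (0.631/r − 1)C.

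At r = 0.5 (a 0.30 log10 loss, which should fail), the factors are 0.131 and 0.262:

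| C (CFU/mL) | b, native unaffected | b, killed in proportion |
|---|---|---|
| 30 | 3.9 | 7.9 |
| 50 | 6.5 | 13.1 |
| 100 | 13.1 | 26.2 |

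Worse neutralizers need more. At r = 0.3 the factors are 0.331 and 1.10. At r = 0.1 they are 0.531 and 5.3. At C = 50 that is 16.5 or 55 CFU/mL, and 26.5 or 265 CFU/mL.

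**On the skin scale.** Cup area and fluid volume are redacted. Assuming 1 to 2 mL of fluid per cm², the r = 0.5 range of 3.9 to 26.2 CFU/mL is about 4 to 52 CFU/cm². The appendix's own background figure is: "The density of normal human skin flora generally ranges from 10² to 10⁵ CFU/cm² depending on the body site". That describes untreated skin. How much remains depends on the combined effect of swab and treatment, for which the documents give no figure. From 10³ CFU/cm², for example, a 2 log10 reduction leaves 10 CFU/cm² and a 3 log10 reduction leaves 1.

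**Chance of a pass.** A Poisson simulation used three plates per replicate, 1 mL plated, three Test 3 replicates (8.2.3) and four Test 1 replicates (assumed). At C = 50 and r = 0.5, with b counted as surviving native colonies:

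| b (CFU/mL) | 0 | 3 | 5 | 10 |
|---|---|---|---|---|
| Pass probability | 0.0% | 4.7% | 23% | 93% |

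With no native colonies, the pass probability at r = 0.5 is about 0.7% at C = 30 and under 0.1% at C = 50 or 100. The criterion separates well when the background is absent.

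**What a missed 50% loss would mean.** As an illustration, 0.30 log10 in one active only is 0.30/0.5 = 60% of the non-inferiority margin. Against vehicle it is 0.30/1.2 = 25% of the superiority margin.

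**The case against.** The strongest reply is that the plan does act on native flora. Three alcohol swabs and a full treatment application precede the washing, and the stated purpose of the swabs is to ready the skin for this test. Residual flora should be lowest after the two actives, where neutralization matters most, and highest after vehicle, where it matters least. Native cells must also survive un-neutralized residue in the tube. The criterion uses mean log10 counts, so one contaminated washing has limited effect. All of this stands, and it lowers the chance of a harmful false pass. It does not show that the washings are clean.

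Four stronger readings are tempting, and the documents do not support them:

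- **Nothing removes native flora.** Section 7 contradicts this. The gap is that removal is not verified.
- **Trial baselines of 3.0 to 5.5 log10 show that enough flora remain.** That range (Table 3.2) applies to abdominal efficacy sites. Validation subjects have no minimum count and may shower, both of which point to lower counts.
- **Even a neutralizer with zero recovery could pass.** Native cells would have to survive residue that kills every challenge cell. If both are killed in the same proportion, zero recovery can never pass.
- **Test 1 is the only protection against carry-over.** Section 5.2.3 also puts neutralizers in the diluent and the agar and requires plating within 30 minutes. Test 1 is verification.

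The appendix also cites an external neutralization standard and laboratory methods that may add controls. Those are not available here, so the point concerns what the appendix itself lists.

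**Conclusion.** The gap is real and its direction is certain: on the criterion as written, residual native flora can only move Test 1 towards a pass, and nothing listed would detect or correct this. The only size fixed by the documents is the 63.1% threshold. The 4 to 13 and 8 to 26 CFU/mL figures rest on an assumed inoculum of 30 to 100 CFU/mL, and the pass probabilities also rest on assumed replicate numbers.

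A reader might infer that the neutralizer is inadequate, or that the 30-second results would be biased. Neither follows. A false pass is possible but not shown to be likely, and its likelihood cannot be estimated from the redacted text. This is an inexpensive improvement to the only stated verification of neutralization, and the change is worth making for that reason.

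**What to change.** - **8.2.1:** plate triplicate un-inoculated aliquots of the remaining portion of each washing on TSA+N at the same two times (within one minute and at 30 minutes). Add the same volume of organism-free PBW so that dilution matches. These aliquots meet the same residue as Test 1, so the subtraction holds whether or not native cells are being killed.
- **8.4(a) and (d):** subtract the native count from the Test 1 count on the CFU/mL scale, before taking log10, and compare the result with Test 3. State in advance how a difference of zero or below is handled.
- **Report** the native count by treatment, which also shows whether the alcohol step worked.

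The cost is six extra plates per washing (three plates at two times), provided enough washing is left. Only a portion is inoculated, but the volumes are redacted. No extra subject or repeat skin sampling is required. Test 1 becomes slightly more variable. With 35 total and 10 native colonies expected per plate, the Poisson standard deviation of the three-plate result rises from √(35/3) = 3.4 to √(45/3) = 3.9.
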